	
Secondary Endpoint 3:          Cumulative duration of response, i.e., total time in response from the first achievement of an Overall Response until EOT
	
Estimand 2.3          Target population: All patients received at least one infusion of IMP excluding those who do not achieve response at least once between the date of first dose and EOT          Treatment: Refer to Section 6.4 in study protocol          Endpoints: Refer to the left column          Strategies for addressing intercurrent events:          The treatment policy strategy will be applied for the estimand          Population-level summary:          Duration of response will be estimated using descriptive statistics

	
Secondary Endpoint 4:          Ability to reduce glucocorticoids by 50% or more of the baseline dose during emapalumab treatment
	
Estimand 2.4          Target population: All patients received at least one infusion of IMP          Treatment: Refer to Section 6.4 in study protocol          Endpoints: Refer to the left column          Strategies for addressing intercurrent events:          The treatment policy strategy will be applied for the estimand          Population-level summary:          Number and percentage of patients able to reduce glucocorticoids by 50% or more of the baseline dose during emapalumab treatment

	
Secondary Endpoint 5:          Investigator assessed response
	
Estimand 2.5          Target population: All patients received at least one infusion of IMP

		
Treatment: Refer to Section 6.4 in study protocol
 
Endpoints: Refer to the left column
 
Strategies for addressing intercurrent events:
 
The treatment policy strategy will be applied for the estimand
 
Population-level summary: Investigator’s assessment of clinical response up to HSCT will be estimated using descriptive statistics

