#### **6.2.2. Derivation and Transformation on Data**

Besides the calculation for certain endpoints (as listed below), which are based on data collected via CRF, no derivation or transformation will be applied. Outliers will be reported to data management function as a data issue to be resolved or confirmed before database lock. No special data handling will be done.

For the derivation of the achievement of Overall Response, refer to [Section 6.8.2](#).

Age (in years) = (Date of informed consent/assent – birth date + 1)/365.25, rounding up to integer;

Time to first overall response (in days) = Date of the first achievement of response (Complete Response, Partial Response or HLH Improvement) – date of the first dose of emapalumab + 1, patients without a response will be censored at the date of EOT visit or last assessment;

Cumulative duration of response (in days) = Date of EOT visit – date of the first achievement of response + 1, for patients who achieve a response, lost that response, and then achieve any response subsequently, the total time in response will be calculated by adding together these separate periods in response;

Survival to start of HSCT conditioning (in days) = Date of death – date of first dose of emapalumab + 1, patients with no event will be censored at date of the start of conditioning for HSCT or last contact for patients who did not undergo HSCT;

Survival after HSCT (in days, calculated only for patients underwent HSCT) = Date of death – HSCT performed date+ 1, patients with no event will be censored at date of last contact;

Overall survival (in days) = Date of death – date of first dose of emapalumab + 1, patients with no event will be censored at date of last contact;

Dose administered (mg) = Prescribed dose [mg] × Approximate Proportion Administered [%];

Total duration of dosing (days) = Date of last infusion – date of first infusion + 1;

Average dosing frequency (times per day) = The total number of records of emapalumab infusion / total duration of dosing;

Prescribed dose change from first dosing (%) = (Prescribed dose at visit [mg] - prescribed dose at first dosing [mg]) / prescribed dose at first dosing [mg] × 100%.

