#### Cumulative Duration of Response

The treatment policy strategy will be applied. The cumulative duration of response will be estimated as described below regardless of any potential intercurrent events.

Cumulative duration of response is defined as total time in response from the first achievement of an Overall Response until EOT ([refer to Section 6.2.2](#)). For patients who achieve a response, lost that response, and then achieve it subsequently, the total time in response will be calculated by adding together these separate periods in response. The cumulative duration of response will be calculated under the hypothetical assumption that a patient's response achieved at any visit will maintain up until the next visit. Patients who do not achieve response at least once between the date of first dose and EOT will be excluded from the analysis. Cumulative duration of response will be summarized using descriptive statistics.

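### The SAP 6.2.2 formula for cumulative duration of response conflicts with the endpoint's definition and with the SAP 6.8.2 visit rule for patients who lose response for good

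*SAP*

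**What the plan says.** SAP 6.2.2 gives the only explicit formula: "Cumulative duration of response (in days) = Date of EOT visit – date of the first achievement of response + 1". It makes one exception: "for patients who achieve a response, lost that response, and then achieve any response subsequently, the total time in response will be calculated by adding" the separate periods together.

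SAP 6.8.2, under Cumulative Duration of Response, starts from a definition: "Cumulative duration of response is defined as total time in response from the first achievement of an Overall Response until EOT". It refers back to 6.2.2 and repeats the exception ("For patients who achieve a response, lost that response, and then achieve it subsequently"). It then adds a general assumption that is not limited to patients who regain response: "a patient's response achieved at any visit will maintain up until the next visit". Patients who never respond are left out of the analysis, and the rest are summarised descriptively.

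The estimand table in SAP section 3 has the same definition: "Cumulative duration of response, i.e., total time in response from the first achievement of an Overall Response until EOT".

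The protocol also defines the endpoint as total time in response, but gives two ends for the window. Section 5.2.1 uses EOT. Sections 8.3.4 and 8.3.4.1 use the earlier of EOT and week 8. SAP section 9, which lists changes from the protocol's analysis plan, names the supplementary response analysis and overall survival, but not this difference.

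No section states the value for a patient who responds, loses response and never regains it.

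**The concern.** The 6.2.2 formula measures the time from first response to EOT. That equals time in response only if response is never lost. The exception corrects it for patients who lose and regain response. A patient with permanent loss is outside the exception, so a programmer working from 6.2.2 would count all the days without response up to EOT. A programmer working from the 6.8.2 visit rule would stop counting at the first visit without response.

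The case is foreseeable. Protocol 6.4.5.2.3 and 6.5.1.3 both describe worsening or reactivation while emapalumab continues, and protocol 6.4.4 allows treatment of up to about 6 months, so EOT can fall well after the loss. At stake is whether the reported duration separates a lasting response from one that failed on treatment. With 10 to 18 patients planned, one or two such patients can move the summary.

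**Working it through.** The plan states no figure for this endpoint, so there is nothing to reproduce. The check applies both derivations to the same patients.

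**Inputs from the documents**
- Formula and exception: SAP 6.2.2.
- Visit rule: SAP 6.8.2.
- Visits twice weekly, at most 4 days apart, with EOT 3±1 days after the last infusion: protocol 6.5.1.3.

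**Assumptions for illustration**
- Visits on days 0, 3, 7, 10, 14 and so on, and EOT exactly 3 days after the last infusion.
- First response on day 7, with loss first seen on day 28.

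**Formulas**
- 6.2.2 as written: EOT − first response + 1, unless response is lost and regained.
- 6.8.2 visit rule: each visit in response counts until the next visit. One day is added if the patient is in response at EOT.

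**Three patients, EOT on day 59**

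| Patient | 6.2.2 as written | 6.8.2 visit rule |
|---|---|---|
| Sustained from day 7 | 59 − 7 + 1 = 53 | (59 − 7) + 1 = 53 |
| Lost for good at day 28 | 59 − 7 + 1 = 53 | 28 − 7 = 21 |
| Lost at day 28, regained at day 52 | (28 − 7) + (59 − 52) + 1 = 29 | 29 |

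Under the literal formula, permanent loss scores the same as a sustained response and 53 − 29 = 24 days more than a response that is regained. The third row counts the extra day once. The SAP does not say whether it applies to each period; if it did, that value would be 30, and the ordering would not change.

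**Permanent loss at day 28, by EOT date**

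| EOT day | 6.2.2 as written | Visit rule | Difference |
|---|---|---|---|
| 31 | 25 | 21 | 4 |
| 59 | 53 | 21 | 32 |
| 87 | 81 | 21 | 60 |
| 185 | 179 | 21 | 158 |

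For sustained responders the two derivations agree at every EOT date (25, 53, 81 and 179). If loss is first seen on day 14 instead, the visit rule gives 14 − 7 = 7 days.

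**Effect of the window end.** If the window closes at week 8 (day 56), the literal formula gives at most 56 − 7 + 1 = 50 days for permanent loss at day 28, against 21. The difference is then at most 29 days, however late EOT falls.

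**Effect on a group mean.** Assume 10 responders, one of whom has this pattern. The mean rises by 32 / 10 = 3.2 days with EOT on day 59. The range over the EOT dates above is 4 / 10 = 0.4 to 158 / 10 = 15.8 days.

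**The case against.** The strongest reply is that the SAP already has the right rule. Section 6.8.2 defines the endpoint as total time in response, and its assumption that a "response achieved at any visit will maintain up until the next visit" applies to every responder. On that reading credit stops at the first visit without response, and the permanent loser in the illustration gets 21 days whatever the EOT date. This stands to the extent that the plan as a whole cannot be said to prescribe credit up to EOT. It does not remove the problem. Section 6.8.2 sends the reader back to 6.2.2 for the calculation and repeats the lose-and-regain exception. That exception would be unnecessary if the visit rule were meant to govern everyone.

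A reader might also infer that about a quarter of responders would be affected, because protocol 4.3.1 says that 75% of earlier patients maintained their first response for at least 22 days. The documents do not support this. They do not say that the other patients lost response for good, and they do not exclude that some regained it or were observed only briefly. Any simulated group mean built on a 25% permanent-loss rate and an assumed spread of EOT dates rests on inputs the plan does not give.

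The large differences need a patient with no response of any category, HLH Improvement included, for months while still on treatment. The 158-day case is an extreme.

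Finally, the endpoint is secondary and descriptive, no hypothesis is tested, and the primary endpoint and Overall Response are untouched. That limits severity, but does not say which of the two values should be reported.

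**Conclusion.** The concern holds as an inconsistency. The explicit formula in SAP 6.2.2 contradicts both the endpoint's definition and the visit rule in 6.8.2, and permanent loss of response is not addressed. The reported value depends on which section is programmed: 53 or 21 days in the main illustration.

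Two stronger conclusions do not follow: that the plan requires credit up to EOT, and that the endpoint cannot tell lasting from transient response. Both are true only if the 6.8.2 visit rule is set aside.

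Severity is moderate. Only patients with permanent loss on treatment are affected, and the documents do not say how many to expect. The day counts rest on assumed visit, loss and EOT dates. They show the direction and possible size of the discrepancy, not an expected bias. The unreconciled window end adds to the uncertainty, because it determines how large the over-credit can be.

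**What to change.** Replace the 6.2.2 formula with one rule for all responders:

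- Sum the intervals in response. Each runs from the first visit in response to the earlier of the next assessed visit without response and the window end, whether or not response is later regained.
- Add the final day (+1) at most once, and only if the patient is in response at the window end. A patient who first responds at EOT then scores 1 day.
- Count no time after EOT.
- Delete the lose-and-regain exception from 6.2.2 and 6.8.2, since the rule covers it.

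At the same time, choose one window end. SAP 6.2.2 and 6.8.2 and protocol 5.2.1 use EOT; protocol 8.3.4 and 8.3.4.1 use the earlier of EOT and week 8. If EOT is kept, record the departure from protocol 8.3.4 and 8.3.4.1 in SAP section 9. If the earlier of the two is chosen, use it as the window end in the rule above.

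The cost is a few sentences in the SAP and a small program change, best made before the response algorithm is run after database lock. The downside is that, compared with the literal formula, the reported duration becomes shorter for patients who lose response on treatment.

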6.1 Overall study design and plan

This is an open-label, single-arm, multi-centre study to collect safety and efficacy data on emapalumab in treatment experienced male and female patients diagnosed with pHLH. The study will be performed in China.

The study will recruit at least 10 patients, and up to 18 patients if enrolled within the recruitment period.

Patients should already have received conventional HLH therapy (treatment experienced patients), without obtaining a satisfactory response according to the investigator or having shown signs of intolerance to it.

Figure 1 summarizes the study design.

The study is divided into three parts: screening, treatment period, and follow-up. Patients will be admitted to the unit the day before the first administration of the study drug (study day minus one, SD-1).

Figure 1 Overview of the study design

SCREENING	TREATMENT					FOLLOW-UP					
Day -14 to Visit 1	Visit 1 (SD 0)	Visit 2 (SD 3-4 and onwards) every 3-4 days	W8 Primary assessment timepoint if treatment continues	W9-onwards until start of conditioning for HSCT	EOT (3±1 day after last infusion) Primary assessment timepoint if treatment stopped before week 8	Pre-HSCT		Post HSCT			
	Initial dose	Subsequent doses				Pre-conditioning	W 1/2/3	D 30	D 60	D 100	M6

Abbreviations SD, study day; EOT, end of treatment; HSCT, hematopoietic stem cell transplant; W, week; D, day after HSCT; M, month; EOS, end of study

The patient will enter screening after informed consent is obtained and will undergo screening assessments to confirm eligibility. Duration of the screening period will be kept as short as possible and should not exceed 2 weeks.

First emapalumab infusion, at a dose of 1 mg/kg, marks the start of the treatment period. The treatment period is foreseen to continue until start of conditioning for HSCT, if deemed indicated for this patient. Infusions will take place twice weekly, at a dose determined by the Investigator for each infusion, as described in Section 6.4.4. Emapalumab will be administered on the background of dexamethasone, which can be tapered or increased as needed. No wash-out is required prior to conditioning for HSCT.

Last visit of the treatment period is the end of treatment, which occurs 3 days after the last infusion of emapalumab. Assessment of efficacy objectives occurs at end of treatment.

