6.3.3 Withdrawal of patients from treatment or study

6.3.3.1 Withdrawal from treatment or study

A patient should be withdrawn from the study for any one of the following reasons:

- if, in the opinion of the investigator, it is medically necessary
- if the patient or their legally authorized representative(s) withdraws consent
- if the patient enrolls into an interventional clinical study in which an investigational treatment or approved therapy for investigational use is administered

There are no predefined rules for permanent study drug discontinuation based on the current safety profile of the drug. The Investigator can decide to interrupt or discontinue the treatment for his/her patient at any time during the study, based on his/her medical judgment taking into account the individual benefit/risk ratio for the patient. The Investigator may request a discussion with the Sponsor, if relevant prior to taking a decision; however, the ultimate decision remains the Investigator's responsibility.

Pregnancy in a patient will lead to permanent discontinuation of study treatment.

The date of last IMP dose and the date and reason for treatment and/or study withdrawal should be clearly described in the relevant sections of the eCRF. If a patient is withdrawn because of an AE, the reason for withdrawal should always be stated as 'adverse event' irrespective of whether this was the investigator's or the patient's decision. All serious and non-serious AEs assessed by the investigator as related to the IMP should continue to be followed until they resolve or until the investigator assesses them as "chronic" or "stable", even after the patient's participation in the study is over, but without further recordings into the eCRF.

After treatment discontinuation for any reason, patient should be invited to continue the follow-up period in the study, and every effort should be made to obtain the data collected at the End of Treatment and the follow-up visits as complete as possible.

In any case, withdrawal from the treatment and/or study will have no impact on the patient's care and on further standard of care treatments administered to him/her after withdrawal.

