6.5 Safety and efficacy assessments

6.5.1 Study schedule

All visits should take place as close to planned dates as possible. Infusions should not take place more than 4 days apart. Detailed information on assessments and timing could be found in Sections 6.5.2 - 6.5.8 and Table 3 and Table 4

In the follow-up period, the following time-windows are allowed:

Pre-conditioning: can be combined with EOT visit provided the two visits are not more than 5 days apart

- Week (W) 1-2-3, Day+30 post-HSCT: ± 2 days
- Day+60, Day+100 post-HSCT: ± 1 week

- 6-months, 1-year post-HSCT: ± 4 weeks

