6.5.1.4 Follow-up period

After treatment completion or treatment discontinuation (for any reason), patients will continue in the study for long-term follow-up until 1 year after either HSCT or last emapalumab infusion (if HSCT is not performed). This will represent the last visit in the study. If search for a donor is longer than 6 months, the follow-up period will be reduced, and the EOS will take place no later than 18 months after the first dose of emapalumab.

A patient who experiences HLH reactivation during the follow-up period, may be re-treated with emapalumab.

After the patient has completed the EOS visit, they should be treated and followed-up according to investigator judgment and local practice. No further investigational medicinal product will be provided.

In case of an ongoing SAE, the patient will continue to be monitored until resolution or until the outcome of the event is known and stable, beyond the defined study end as necessary.

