### All treated analysis set

All treated analysis set comprises all patients who received at least one infusion of IMP.

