## **6.5. Exposure and Compliance**

IMP administration including level of dose prescribed, prescribed dose, date, time and duration of dose administration, and information on dose increase and dose interruption will be collected in the CRF.

The total prescribed dose, total dose administered, total duration of dosing (in days), and average dose frequency (times per day) will be summarized using descriptive statistics. The dose administered will be calculated based on prescribed dose and approximate proportion administered (refer to [Section 6.2.2](#)). The total duration of dosing will be calculated based on the date of last infusion and the date of first infusion (refer to [Section 6.2.2](#)). The average dosing frequency will be calculated based on the total duration of dosing and the total number of records of emapalumab infusion (refer to [Section 6.2.2](#)).

The emapalumab dose change from the first dosing will be summarized showing the number and percentage of patients with a dose increase or a dose decrease at each visit. Moreover, the percentage of dose increases and decreases from the first dose for each patient will be summarized using a descriptive table. Percentage of dose increase or decrease from first dose will be calculated based on prescribed dose at first dosing and prescribed dose at each visit (refer to [Section 6.2.2](#)).

Data listing containing all information collected for IMP administration will be provided. In addition, IMP administration will be listed at patient level including all dose adjustments over time and summarized in terms of the number of doses administered, maximum dose, equivalent dose of dexamethasone, duration of exposure from the first dose to the last dose of treatment, cumulative dose, average dose frequency and average dose per day.

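### The average dosing frequency formula inflates short courses, shows a single missed infusion only weakly, and would count the gap before re-treatment as dosing time

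*SAP*

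**What the plan says.** SAP 6.2.2 gives two linked derivations. The denominator is "Total duration of dosing (days) = Date of last infusion – date of first infusion + 1", and the frequency is "Average dosing frequency (times per day) = The total number of records of emapalumab infusion / total duration of dosing". SAP 6.5 (Exposure and Compliance) repeats the rule, "The total duration of dosing will be calculated based on the date of last infusion and the date of first infusion", and summarizes both quantities descriptively. Neither section has a rule for a patient with one infusion or for more than one course.

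On the schedule, Protocol 6.1 states "Infusions will take place twice weekly, at a dose determined by the Investigator for each infusion", Protocol Table 1 gives a 3-4 day interval, and Protocol 6.5.1 adds "Infusions should not take place more than 4 days apart". Short courses are in scope: "All treated analysis set comprises all patients who received at least one infusion of IMP", and under Protocol 6.3.3.1 "The Investigator can decide to interrupt or discontinue the treatment for his/her patient at any time during the study". A second course is also possible. Protocol 6.5.1.4 says "A patient who experiences HLH reactivation during the follow-up period, may be re-treated with emapalumab".

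**The concern.** A run of n infusions contains n - 1 dosing intervals. The SAP counts all n in the numerator but adds only one day to the span, where the last infusion would need a further interval of 3 or 4 days. The ratio therefore exceeds the rate at which the patient was actually dosed, most of all when treatment stops early. For a single infusion it returns one per day, which no schedule in the protocol could produce.

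The same excess offsets a missed infusion, so the figure says little about adherence. SAP 6.5 nevertheless carries compliance in its title and offers no other summary of schedule-keeping.

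The first-to-last rule also treats time off drug as dosing time if a second course is given. SAP 6.2.2 allows no derivation beyond those it lists, so a programmer has no instruction to separate courses. Yet the same section adds separate periods together for cumulative duration of response.

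At stake is the exposure context for the safety data. With 10 to 18 patients, one unusual course can move a mean visibly.

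**Working it through.** The documents state no numerical dosing frequency, so there is no figure to reproduce. The check applies the SAP formula to constructed schedules.

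**Inputs.** Planned rate: 2 per 7 days = 0.286 per day (Protocol 6.1). Every 3-4 days corresponds to 1/4 = 0.25 up to 1/3 = 0.333 per day (Protocol Table 1). The limit between infusions is 4 days (Protocol 6.5.1). Course lengths, missed-infusion patterns and re-treatment gaps are assumptions.

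**1. Full adherence, days 0, 3, 7, 10, ...** SAP frequency = n/(last - first + 1).

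| n | Last day | SAP frequency | Ratio to 2/7 |
|---|---|---|---|
| 1 | 0 | 1/1 = 1.000 | 3.50 |
| 2 | 3 | 2/4 = 0.500 | 1.75 |
| 4 | 10 | 4/11 = 0.364 | 1.27 |
| 8 | 24 | 8/25 = 0.320 | 1.12 |
| 16 | 52 | 16/53 = 0.302 | 1.06 |
| 52 | 178 | 52/179 = 0.291 | 1.02 |

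Effect on a mean, assuming every other patient has 16 on-time infusions: one single-infusion patient moves it from 0.302 to (9 × 0.302 + 1)/10 = 0.372 with 10 patients, or (17 × 0.302 + 1)/18 = 0.341 with 18.

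**2. One interior infusion missed.** On an alternating schedule this leaves a 7-day interval.

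| Schedule | Planned | SAP frequency |
|---|---|---|
| 3/4 days | 4 | 3/11 = 0.273 |
| 3/4 days | 8 | 7/25 = 0.280 |
| 3/4 days | 16 | 15/53 = 0.283 |
| 4/3 days | 8 | 7/26 = 0.269 |
| every 3 days | 8 | 7/22 = 0.318 |
| every 4 days | 8 | 7/29 = 0.241 |

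All but the last lie within 0.25 to 0.333. Two infusions missed out of eight on the 3/4-day schedule do show: 6/25 = 0.240.

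**3. Re-treatment.** Assume 16 infusions (days 0 to 52), a gap of G days from the last infusion of the first course to the first of the second, then 8 infusions spanning 24 days. SAP duration = 52 + G + 24 + 1 = 77 + G. The two courses taken separately last 53 + 25 = 78 days.

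| G (days) | SAP duration | SAP frequency |
|---|---|---|
| 30 | 107 | 24/107 = 0.224 |
| 90 | 167 | 24/167 = 0.144 |
| 180 | 257 | 24/257 = 0.093 |

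**4. Alternative, (n - 1)/(last - first) within course.** Sixteen on-time infusions: 15/52 = 0.288. The re-treated patient: (15 + 7)/(52 + 24) = 22/76 = 0.289, whatever the gap. Sixteen planned with one interior infusion missed: 14/52 = 0.269, still within 0.25 to 0.333. The alternative removes the short-course and gap errors, but does not by itself reveal one missed infusion.

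**The case against.** The strongest reply is that nothing depends on this number. It is not an endpoint, feeds no estimand, and is never compared with a planned rate or a threshold. SAP 6.1 also reports median, quartiles and range, so an extreme value would be visible and the median little affected. SAP 6.3 tabulates important deviations and lists all of them, and SAP 6.5 lists every administration, so in a study of this size a reader could see each gap directly. All of this stands and limits the severity. It does not make the summary correct as labelled.

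Three stronger readings are tempting and fail.

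- A reader might infer that a missed infusion is scored as exactly on schedule. Infusions on days 0 and 6 do give 2/7, but that is a chosen case. Missing the middle infusion of days 0, 3, 7 gives 2/8 = 0.25, which is 88% of 2/7.
- A reader might infer that a compliant patient always scores above 2/7. A patient dosed every 4 days throughout scores 8/29 = 0.276 and 16/61 = 0.262. Both exceed that patient's own rate of 0.25 but fall below 2/7.
- A reader might infer that primary-endpoint events will show the highest frequencies. Discontinuation can come at any time. The serious infusion reaction described in Protocol 4.3.2, which led to discontinuation, occurred during the eighth infusion, where a 3/4-day schedule gives 0.320.

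The re-treatment part is conditional. Protocol Table 4 has no infusion row, and the documents do not say whether re-treatment infusions enter the same dataset; they do not exclude them either. SAP 6.5 gives no formula for average dose per day, so no effect on that quantity can be claimed.

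**Conclusion.** The point holds as a minor defect in a descriptive exposure summary. As written, the formula overstates frequency in short courses: 3.5 times the planned rate for one infusion and 27% above it for four, falling to about 6% at 16 infusions and 2% at 52. These figures assume an alternating 3/4-day schedule. The measure is a weak indicator of adherence because one missed interior infusion usually stays within the every-3-4-days range, although a strict 4-day schedule or several misses in a short course can fall outside it. If re-treatment occurs and is pooled with the first course, the measure fails in the opposite direction: with the assumed courses, frequency falls to between 79% and 33% of 2/7 (0.224 to 0.093) for gaps of 30 to 180 days, with every infusion on time within its course. The documents support no inference that the primary endpoint, an efficacy result or a study conclusion is affected.

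**What to change.** In SAP 6.2.2 and 6.5:

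- Calculate dosing frequency within course as (n - 1)/(last - first infusion date). Report single-infusion patients separately as not calculated.
- Define a course, for example by letting emapalumab resumed after the EOT visit open a new one. Sum total duration over courses and show re-treatment separately.
- Add how many patients, and what percentage, had any within-course interval above the protocol's 4 days. This is needed because the revised rate alone does not detect a single missed infusion.

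The cost is SAP wording and minor programming. Infusion dates are already recorded (Protocol 6.4.6, SAP 6.5), and no endpoint or dosing rule changes.
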